Families were stratified (by recruitment site and self-identified race/ethnicity of the Index Adult) and randomized to the Health Coach group or the Education Only group in a 1:1 ratio by the Community Resource Specialist. A computer algorithm was used to randomize the families, and the Community Resource Specialist then discussed the results with the family and schedule the next step. Thus, Data Collectors were blinded to group assignment.

7. Study Conditions

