The trial design includes three factors: 1) two treatment groups (control, intervention), 2) four time points (0, 6, 12, and 18), and 3) two age groups (adult, child). Each variable will be summarized by descriptive statistics, including mean, standard deviation and quartile at each time point (separately by treatment and age groups). Index Adults and Index Children will be analyzed separately. Outcomes have repeated measures at multiple time-points. The primary analysis compares the change in primary outcomes from baseline to 12 months between the treatment groups to gauge the efficacy of the intervention. The secondary analysis compares both the 6- and 18-month average change from baseline between the two treatment groups to assess short-term effect and longer-term sustainability. The analysis will be based on intention-to-treat and use two-sided t-test for the primary outcomes with multiple imputation to account for missing values. Multiple imputation models will incorporate 6-month values when available. Linear mixed models for repeated measures will be used for other analysis using multiple time points.

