9.1. Power

Power calculations were based on data from the pilot intervention and information culled from related trials. See Table

Table 6. Power calculation	Standard deviations	Difference	80% power ^a	Assuming 30% dropout	Source
Adults BMI change	Intervention 2.29 ^b Control 2.28	1 kg/m ²	65 per group	92 per group	Wadden (2011) ¹³⁶
Adult Accelerometer	Intervention 101.9 ^c Control 77.7	35-minutes	82 per group	117 per group	Napolitano (2010) ¹³⁷
Children Accelerometer	59.4 for both ^d	30-minute	50 per group	71 per group	Robertson (2011) ¹³⁸
FNPA	5.1 for both ^e	2 points	81 per group	116 per group	Ihmels (2009) ¹¹⁹

^a Using a two-sided 0.05-level two-sample t-test

^b Pilot data at 6 months showed a SD 1.98 – We used Wadden's numbers to be conservative

^c The intervention group had baseline and 12-month SD's of 44.2 and 59.6, while the control group had SD of 42.5 and 44.6. No information was available on the SD of the baseline-to-12-month change. Taking the most conservative approach, we computed the largest possible pre-post SD and found the largest possible baseline-12 month SD's (101.9 intervention, 77.7 control)

^d Table 1 reported baseline-to-9 months CI's. From these, we computed a 0-9 month SD of 59.4 to use for the 0-12 month change

^e For those with income <\$25,000. Our pilot showed a similar number of SD 5.4 for change at 6 months

Based on these power calculations, a target of 260 families was to be recruited to account for dropout prior to randomization, following randomization, and throughout all timepoints of the intervention.

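### The FNPA row of Table 6 claims 80% two-sided power at 81 per group; its own inputs give about 70%, and about 65% at the pilot's change SD

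*Combined protocol and SAP*

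**What the plan says.** Section 2 lists the FNPA score among the Index Child primary outcomes. The Data Analysis Plan (section 9) fixes the comparison: "The primary analysis compares the change in primary outcomes from baseline to 12 months between the treatment groups". It says the analysis will "use two-sided t-test for the primary outcomes with multiple imputation to account for missing values". Allocation is 1:1 (section 6).

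In section 9.1, the FNPA row of Table 6 uses SD 5.1 in both groups and a 2-point difference. It gives 81 per group for 80% power, and 116 per group in the column headed "Assuming 30% dropout". Footnote a names the test for the whole table: "Using a two-sided 0.05-level two-sample t-test".

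Footnote e describes the source of the 5.1: "For those with income <\$25,000". It then reports the trial's own experience: "Our pilot showed a similar number of SD 5.4 for change at 6 months". Footnote b deals with the same choice for adult BMI: "Pilot data at 6 months showed a SD 1.98", and there the plan used the larger external SD (2.29 and 2.28) on grounds of caution. Footnote c likewise takes the largest SD possible for adult accelerometry.

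The recruitment target is 260 families, which is also meant to cover losses before randomisation.

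**The concern.** Two features of the FNPA row do not fit the rest of the plan. First, 81 per group looks small for a standardised difference of 2/5.1 = 0.39 under a two-sided 5% test. Second, where an external SD and a pilot SD were both available, the BMI row took the larger and the FNPA row took the smaller, with no reason beyond calling the two similar.

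The FNPA requirement of 116 per group is one below the largest in the table (117, adult accelerometer), so it helps set the recruitment target. If the stated power is too high, a null FNPA result will be read as coming from a trial with 80% power to detect 2 points when the real figure was lower.

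**Working it through.** **Inputs.** Difference d = 2; SD s = 5.1 (Table 6) or 5.4 (footnote e); alpha 0.05, two-sided (footnote a and section 9); power 80%; 1:1 allocation; dropout 30%.

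**Formula.** Normal approximation: n per group = 2 × [s × (z_alpha + z_beta) / d]², with z_beta = 0.8416 and z_alpha = 1.9600 (two-sided) or 1.6449 (one-sided). Each result was checked with the noncentral t.

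**Step 1: reproduce the plan's figure (s = 5.1).**
- Two-sided: 2 × (5.1 × 2.8016 / 2)² = 102.1, so 103 per group (104 by noncentral t). The stated 81 is not reproduced.
- One-sided: 2 × (5.1 × 2.4865 / 2)² = 80.4, so 81 per group (81.1 before rounding by noncentral t). This matches.
- Dropout: 81/0.7 = 115.7, so 116. This reproduces.

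The other rows show the same pattern, with ranges running from normal to t:

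| Row | Stated n | One-sided n | Two-sided n |
|---|---|---|---|
| Adult BMI | 65 | 65–66 | 82–83 |
| Adult accelerometer | 82 | 83–84 | 106–107 |
| Child accelerometer | 50 | 49–50 | 62–63 |
| FNPA | 81 | 81–82 | 103–104 |

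**Step 2: substitute the pilot SD (s = 5.4).**
- Two-sided: 2 × (5.4 × 2.8016 / 2)² = 114.4, so 115 per group (116 by t). With dropout, 116/0.7 = 165.7, so 166.
- One-sided: 2 × (5.4 × 2.4865 / 2)² = 90.1, so 91 per group. With dropout, 91/0.7 = 130.

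**Step 3: power to detect 2 points (noncentral t).** The best case for completers is 260 × 0.7 / 2 = 91 per group, which assumes that all 260 families are randomised.

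| Completers per group | SD | Two-sided power | One-sided power |
|---|---|---|---|
| 81 | 5.1 | 69.9% | 80.0% |
| 81 | 5.4 | 64.9% | 75.9% |
| 91 | 5.1 | 74.9% | 83.9% |
| 91 | 5.4 | 70.0% | 80.1% |

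**Step 4: split the loss at 81 per group.** From 80.0% (one-sided, SD 5.1) to 69.9% (two-sided, SD 5.1) is 10.1 points, due to the test. From 69.9% to 64.9% is 5.0 points, due to the SD. On the one-sided scale the SD effect is 80.0 − 75.9 = 4.1 points.

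**Step 5: detectable difference at 80% two-sided power (noncentral t).** At 81 per group: 2.26 points (SD 5.1) and 2.39 (SD 5.4). At 91 per group: 2.13 and 2.25.

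**The case against.** The strongest reply is that the SD choice is a disclosed planning judgement and not an error. The two values differ by 6% (5.4/5.1 = 1.06). The pilot figure covers 6 months while the endpoint is at 12, and the pilot's size is not given. Purely as an assumption, a pilot of 50 families would put a 95% interval of about 4.5 to 6.7 around 5.4, and one of 100 families about 4.7 to 6.3. Both contain 5.1, so calling the values similar is fair. The 5.1 also comes from low-income families, which suits the recruitment strategy in section 4. All of this stands, and it is why the SD counts here only as a sensitivity.

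A reader might infer that the SD choice is what breaks the 80% claim. The documents do not support that: the claim already fails at the plan's own 5.1. Nor do they show that 5.4 is the right 12-month SD, which could be higher or lower. A reader might also want a rule that every row take the larger SD. That would change nothing else, because BMI already does so and neither accelerometer row reports a pilot SD.

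A second reply is that the target of 260 absorbs SD 5.4, since 130 per group with dropout is exactly 260. That holds only on one-sided arithmetic, which the plan twice rules out, and only with no loss before randomisation, which the 260 is meant to cover.

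A third is that multiple imputation using 6-month values may recover some information from dropouts. It may, but the documents give no figure. Full recovery, with 116 per group, would give 84% (SD 5.1) or 80% (SD 5.4) two-sided. That is a ceiling, and Table 6 makes its 80% claim for 81 per group.

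**Conclusion.** The concern holds in this form. Under the two-sided test named in footnote a and in section 9, the FNPA row delivers about 70% power at 81 completers per group, not 80%; about 104 per group would be needed. At the pilot change SD the figures are about 65% and 116. Most of the gap, about 10 of 15 points, comes from a sample size that matches a one-sided 0.05 calculation under a two-sided label. The SD adds 4 to 5 points. Preferring the smaller SD is less cautious than footnotes b and c, but it is a judgement that the plan discloses.

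These figures assume equal SDs in the two groups, a 2-point true difference and analysis of completers. The figures for 91 per group (at most 75% and 70%) also assume no loss before randomisation; any such loss lowers them. The documents do not say how 81 was computed, so the one-sided origin is inferred from the match in this row and the near-match in the other three.

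**What to change.** Recompute the FNPA row of Table 6 with the two-sided 0.05 t-test that the plan names, and restate what the planned size delivers:

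- At 81 per group: about 70% power at SD 5.1 and 65% at SD 5.4, or detectable differences at 80% power of about 2.3 and 2.4 points.
- At 91 per group, labelled as the best case with all 260 families randomised and 30% dropout: at most 75% and 70%.

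Show SD 5.4 as the cautious case beside 5.1, and say in footnote e that it is a 6-month value and how many pilot families it rests on. The other three rows follow the same pattern and should be checked against footnote a at the same time.

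The cost is a restated table row and a less favourable power statement. No families are added, and the analysis does not change.
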